Eligible patients will receive a total of 6 ketamine infusions and 5 WET sessions. The primary outcome will be change in PTSD symptom severity assessed by the Clinician-Administered PTSD Scale for DSM-5 (CAPS-5) from baseline (before the first infusion) to 12 weeks from the start of WET. All participants will be assessed until week 12 following the start of WET. They will complete weekly assessments from baseline until 6 weeks from the start of WET, as well as assessments at 12 weeks from the start of WET. At other time points between 6 and 12 weeks, participants will be assessed weekly, or less frequently as tolerated. Although initial response to ketamine (PTSD and co-morbid depressive symptom improvement) will be assessed after the first four infusions (prior to starting WET), all participants will receive 6 infusions and 5 WET sessions regardless of their initial response to ketamine. Participants will be asked not to make any changes to any concomitant treatment (i.e., medication dosages, psychotherapy) during this period.

Thereafter, participants who remain improved at the 12-week time point (compared to baseline) will then receive additional monthly assessments up to 24 weeks or until loss of this improvement.

We will also evaluate whether extinction learning ability –assessed with a computerized extinction learning task– is associated with PTSD symptom improvement from baseline to 12 weeks from the start of WET. If demonstrated to result in significant and maintained PTSD symptom improvement, this novel combined treatment may represent a promising intervention for individuals with chronic PTSD, deserving further study.

Objectives:

Primary Objective: To evaluate the efficacy of adding WET to ketamine therapy in improving PTSD symptoms from baseline to 12 weeks from the start of WET, in individuals with chronic PTSD .

Secondary Objectives (exploratory): (1) To evaluate improvement in PTSD symptoms from baseline to 6 weeks, and on other measures from baseline to 6 weeks, and from baseline to 12 weeks; (2) To evaluate durability of PTSD symptom improvement beyond 12 weeks in patients who remain improved, up to 24 weeks; (3) To evaluate whether ketamine-induced change in extinction learning is associated with improvement in PTSD symptoms from baseline to 12 weeks from the start of WET.

Endpoints:

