Primary Endpoint: Change in PTSD symptom severity assessed by the Clinician-Administered PTSD Scale for DSM-5 (CAPS-5) from baseline to 12 weeks from the start of WET.

Secondary (Exploratory) Endpoints:

- Change in PTSD symptom severity from baseline to 6 weeks from the start of WET, assessed by the CAPS-5.
- Change on other measures, including the Montgomery-Asberg Depression Rating Scale (MADRS), Sheehan Disability Scale (SDS), and Clinical Global Impression severity and improvement (CGI-S and CGI-I), from baseline to 6 weeks, and from baseline to 12 weeks.
- In participants with maintained PTSD symptom improvement after 12 weeks, change on the CAPS-5 and other measures, from baseline to 16, 20, and 24 weeks.
- Additionally, change from baseline to 24 hours after the first ketamine infusion, at each ketamine infusion day, and 24 hours after the 4th infusion, on the Impact of Events Scale (IES-R) and Quick Inventory of Depressive Symptomatology – Self-Report (QIDS-SR), both with past-24-hour recall.

Study Population:	Up to N=15 participants with chronic PTSD will be enrolled in the study. Participants will be aged 18-70 years, male or female, with a current primary diagnosis of chronic PTSD according to DSM-5 and at least moderate current illness severity, as determined by a score of 30 or greater on the CAPS-5. Participants will be recruited from the greater New York City area.
Phase:	2
Description of Sites/Facilities Enrolling Participants:	This will be a single-site study, carried out at the Icahn School of Medicine at Mount Sinai (ISMMS) in New York City, United States.

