1.3 SCHEDULE OF ACTIVITIES (SOA)

Procedures	Screening	Baseline	Ketamine Infusions	24 hour Follow-Up Visit	Assessment of Response to Ketamine	WET Sessions	Weekly Assessment Until 12 weeks	Monthly Assessment Until Loss-of-Response
	Day - 28 to 0	Visit 1a, Day 1	Visit 1a-9; Days 1, 3, 5, 8, 11, 12	Visit 1b, Day 2	Visit 5, Day 9	Visit 6-12, Days 10, 12, 16, 18, 22	Visits 10, 13-23, Days 12, 19, 26...	Visits 23-26, Days 33...
Informed consent	x							
Demographics	x							
Medical history	x							
SCID-5	x							
CAPS-5	x	x			x		x	x
MADRS	x	x			x		x	x
WTAR	x							
MoCA	x							
IES-R		x	x	x	x			
QIDS-SR		x	x	x	x			
PCL-5	x	x			x		x	x
MOS-5		x					x ¹	
CES		x					x ¹	
PACT		x					x ¹	
CTQ	x							
TLEQ	x							
SDS	x	x		x	x		x	x
HMS			x ²					
PIQ			x ²					
C-SSRS	x	x			x		x	x
CADSS		x	x					
BPRS		x	x					
YMRS		x	x					
Extinction Learning Task	x				x			
CGI	x	x	x	x	x		x	x
Concomitant medication review	x	x	x	x	x		x	x
PRISE	x	x	x	x	x		x	x

Adverse event review and evaluation	x	x	x	x	x	x	x	x
Physical exam (including height and weight)	x							
Vital signs	x		x					
Weight	x		x					
EKG	x							
Routine labs	x							
Plasma ketamine and norketamine levels			x ³					
Urine pregnancy test	x		x					
Urine drug screen (UTOX)	x		x					
Ketamine infusion (0.5 mg/kg)			x					
Written Exposure Therapy (WET)						x		
Complete Case Report Forms (CRFs)	x	x	x	x	x	x	x	x

¹Visit 14 and 23 only

²only at Infusions 1 and 2

³only at Infusion 1

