3 OBJECTIVES AND ENDPOINTS

OBJECTIVES	ENDPOINTS	JUSTIFICATION FOR ENDPOINTS
Primary		
To evaluate the efficacy of adding WET to ketamine therapy in improving PTSD symptoms from baseline to 12 weeks from the start of WET, in individuals with chronic PTSD.	Change in PTSD symptom severity, as assessed with the Clinician-Administered PTSD Scale for DSM-5 (CAPS-5), between baseline and 12 weeks following the start of WET.	The CAPS-5 is the gold-standard outcome measure in clinical trials in patients with PTSD. Timing and duration of primary outcome assessment

OBJECTIVES	ENDPOINTS	JUSTIFICATION FOR ENDPOINTS
		were selected based on findings from prior WET and repeated ketamine studies.
Secondary (Exploratory)		
To evaluate longitudinal change in PTSD and depressive symptoms (and clinical global impression and psychosocial functioning) following administration of ketamine infusions and WET, as well as the relationship between change in PTSD and depressive symptoms. All participants will be followed for 12 weeks from the start of WET. To capture any ketamine-related rapid changes in PTSD and depressive symptoms	Change in PTSD symptom severity from baseline to 6 weeks, using the CAPS-5; change in PCL-5, MADRS, CGI, and SDS from baseline to 6 weeks, and from baseline to 12 weeks; in patients with maintained PTSD symptom improvement after 12 weeks, change in PTSD symptom severity from baseline to 16, 20, and 24 weeks.	The CAPS-5 is the gold-standard outcome measure, and the PCL-5 is a self-report measure commonly used in clinical trials for PTSD. The MADRS (depressive symptoms), CGI (clinical global impression), and SDS (psychosocial functioning) are commonly used as well.
	Change in IES-R and QIDS-SR, with 24-hour recall, from baseline to 24 hours after the first infusion, at each infusion day, and 24 hours after the fourth infusion.	These scales are commonly used in clinical trials, including in our 2 previous clinical trials of ketamine for PTSD to capture rapid symptom improvement.
To evaluate whether ketamine-induced change in extinction learning predicts PTSD symptom improvement from baseline to 12 weeks from start of WET.	Performance on Extinction Learning Task following ketamine infusions.	The computerized Extinction Learning Task is sensitive to PTSD. Assessment time point after four infusions (compared to baseline) allows for assessment of maximal change in extinction learning prior to adding WET to ketamine treatment.

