9.4 STATISTICAL ANALYSES

9.4.1 GENERAL APPROACH

Continuous variables will be summarized using the following descriptive statistics: number of non-missing values, means, standard deviations, medians, interquartile range, maximum, and minimum. Categorical variables will be summarized using number of non-missing values, counts and percentages.

Rates of events will be calculated as the ratio of the total number of events recorded divided by the total patient-time. Total patient-time will be calculated by summing the time (in study time units, e.g., days or months) that patients were at risk for a specific event from the reference time point until either study exit or the end of the time period of interest. Rates and their 95% confidence intervals will be reported.

Time-to-event variables will be summarized using the Kaplan-Meier method.

For any variable measured at multiple points in time, change since the day prior to starting WET, “pre-WET” (i.e., the day when response to ketamine is assessed), will be calculated as the difference between the value of the variable at a specific point in time (e.g. 12 weeks) minus the value from pre-WET. Relative change from pre-WET will be calculated as the value of a parameter at a specific point in time minus the pre-WET value of the parameter divided by the pre-WET value of the parameter. Percent change will be calculated as the relative change multiplied by 100.

Should any of the statistical methods proposed prove unsuitable during data analysis, more appropriate methods will be used. These include data transformation (for example to a logarithmic scale) to satisfy model assumptions such as normally distributed residuals with constant variance, the application of non-parametric techniques or the use of a different link function or analytical/modeling technique. The SAP will be updated with the methods used and the justification for the change prior to data set and database lock.

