9.4.3 ANALYSIS OF THE SECONDARY ENDPOINT(S)

- **Secondary Efficacy Outcomes (Exploratory):** In this early-phase study, analyses of secondary efficacy outcomes will be considered exploratory and hypothesis-generating. CAPS-5, PCL-5, MADRS, CGI and SDS scores will be collected weekly through 6 weeks after the start of WET from all

eligible participants, and thereafter until 12 weeks (up to weekly, as tolerated, ensuring assessment at the 12-week time point for all participants). All participants will be followed naturally for 12 weeks from the start of WET, in order to capture, descriptively, more gradual effects of WET and potential effects of the combination of ketamine + WET in all patients. Thereafter, they will be collected monthly through week 24 from start of WET or until loss of treatment response, for the subgroup of participants who demonstrate improvement on the CAPS-5 at the 12-week assessment. Aggregate scores prior to adding WET, during WET, and during the maintenance phase (weeks 3 onward) will be reported descriptively at each time point using the number observed, mean, standard deviation, median, and interquartile range. Individual patient trajectories on these measures will be plotted over time to explore treatment response and patterns in maintenance of response. Mean change in CAPS-5 scores from baseline and corresponding 95% confidence intervals, as well as the proportion of patients with $\geq 30\%$ improvement from baseline on the CAPS-5 will also be reported at each time point. In addition, linear mixed-effects models of these outcomes may be fit to compare mean scores over time. Mixed models will test for the inclusion of a random intercept for patient and fixed effects for week against a fixed intercept model using a likelihood ratio test after comparing each model fit statistic (i.e., Akaike information criterion, AIC) where the best fitting model is the model with the lowest corresponding AIC. Once fit is assessed, parameter interpretation will commence.

- **IES-R and QIDS-SR with past-24-hour recall** – collected only at baseline, before each ketamine infusion, 24 hours after the first infusion, and on the response to ketamine assessment day – will be examined descriptively.

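### Section 9.4.1 defines change only from the pre-WET day, while the listed PCL-5, MADRS, SDS, CGI-S, IES-R and QIDS-SR change endpoints start at the pre-infusion baseline

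*Combined protocol and SAP*

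**What the plan says.** **General rule.** Section 9.4.1 covers "For any variable measured at multiple points in time, change since the day prior to starting WET" and identifies that day with the assessment of response to ketamine. It continues: "Relative change from pre-WET will be calculated as the value of a parameter at a specific point in time minus the pre-WET value", divided by the pre-WET value; percent change is 100 times that. The section has no counterpart from baseline and does not call the pre-WET quantity additional.

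**Endpoint definitions.** The synopsis fixes the meaning of baseline when it states the primary outcome: "from baseline (before the first infusion) to 12 weeks from the start of WET". Section 3 lists "change in PCL-5, MADRS, CGI, and SDS from baseline to 6 weeks, and from baseline to 12 weeks". For participants still improved after week 12, the synopsis adds "change on the CAPS-5 and other measures, from baseline to 16, 20, and 24 weeks". For IES-R and QIDS-SR the synopsis lists "Additionally, change from baseline to 24 hours after the first ketamine infusion, at each ketamine infusion day, and 24 hours after the 4th infusion", and Section 3 agrees.

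**Specific analyses in Section 9.** Sections 9.1 and 9.4.2 give the primary CAPS-5 change from baseline. Section 9.4.3 does the same for secondary CAPS-5 change and for the proportion with at least 30% improvement. For the weekly scales as a group, Section 9.4.3 says "Aggregate scores prior to adding WET, during WET, and during the maintenance phase (weeks 3 onward) will be reported descriptively at each time point", with individual trajectories and optional mixed models. It states no change calculation for PCL-5, MADRS, CGI or SDS. IES-R and QIDS-SR are to be summarised descriptively, with no reference given.

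**Aim 2.** Section 9.4.3 regresses CAPS-5 change at 12 weeks on the change in extinction learning. It does not say where the CAPS-5 change starts, and its heading speaks of maintaining the response to ketamine.

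**The concern.** The general rule and the endpoint lists use different starting points, and for every listed change measure except CAPS-5 the general rule is the only change formula in Section 9. An analyst programming tables from Section 9 could produce MADRS, PCL-5, SDS and CGI-S changes that leave out whatever happened over the first four infusions, and report them under endpoint names that promise change from before treatment.

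For IES-R and QIDS-SR the mismatch is sharper. These scales are included to capture rapid change after the first infusions, and most of their time points come before the reference or coincide with it.

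In a single-arm study of up to 15 participants with no formal testing, the reported change values are the result. A reader must be able to tell what each one is measured from.

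**Working it through.** **1. The plan's own figure.** Section 9.2 gives a 95% confidence interval half-width of 0.5 SD for n = 15. With a normal quantile, 1.96/√15 = 1.96/3.873 = 0.506, which rounds to 0.5. The figure is in units of the SD of the change, so the reference day does not enter it.

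**2. Dates.** The Schedule of Activities (1.3) gives the infusions as "Visit 1a-9; Days 1, 3, 5, 8, 11, 12", the 24-hour visit as Day 2, the response assessment as Day 9 and the first WET session as Day 10. Pre-WET is therefore Day 9, after infusions 1 to 4 (Days 1, 3, 5, 8).

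**3. What the choice of reference changes.** Let B be the baseline score, P the pre-WET score and F a follow-up score.

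- Listed endpoint: F − B
- Rule in 9.4.1: F − P
- Difference: (F − B) − (F − P) = P − B

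The gap is exactly the change from baseline to Day 9. It is the same at every follow-up time for a given participant. For relative change the denominator also moves, from B to P. The documents give no within-arm value of P − B for any scale, so no size can be attached.

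**4. Which measures are exposed.**

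| Measure | Endpoint reference | Reference in the specific text of Section 9 |
|---|---|---|
| CAPS-5, primary and secondary change, 30% proportion | Baseline | Baseline, stated |
| PCL-5, MADRS, SDS, CGI-S | Baseline | None; only the 9.4.1 rule |
| IES-R, QIDS-SR | Baseline | None; only the 9.4.1 rule |

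PCL-5 is named in Section 3 but not in the synopsis list. At weeks 16, 20 and 24 only the synopsis extends to other measures; Section 3 lists PTSD symptom severity alone.

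**5. IES-R and QIDS-SR time points.** The post-baseline days are Day 2 (24 hours after infusion 1), Days 3, 5, 8, 11 and 12 (the later infusion days) and Day 9 (24 hours after infusion 4), seven in all.

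- Before the reference: Days 2, 3, 5, 8, so 4
- At the reference: Day 9, so 1, where change is zero by construction
- After the reference: Days 11 and 12, so 2

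The rule therefore cannot express 4 + 1 = 5 of 7 time points. The count does not depend on the exact dates of the last two infusions, since both follow Day 9.

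**6. Aim 2.** The synopsis, Section 3, Section 4.1 (item f), Section 4.2 and Section 8.1 all give the outcome as baseline to 12 weeks. Only Section 9.4.3 omits the start. Section 9.2 uses similar shorthand for the primary outcome, so an omission is the natural explanation. The gap still matters because the predictor spans baseline to pre-WET, the interval that a pre-WET outcome would remove.

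**The case against.** The best reply is that Section 9.4.1 names a quantity, change since pre-WET, and says how to compute it; it does not forbid change from baseline. Where the plan actually calculates a CAPS-5 change it uses baseline without comment, which favours reading the pre-WET quantity as an extra summary. The endpoint lists are specific and should prevail over a general paragraph. A rule that fails for most IES-R and QIDS-SR time points was plainly not written for them. Scores by time point, trajectories and the optional mixed models do not depend on the reference at all.

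Much of this stands. It makes baseline the likely intent and limits the harm. It does not remove the conflict: the rule is worded for every repeatedly measured variable, has no baseline counterpart, and does not present itself as additional.

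Some stronger readings are not supported:

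- A reader might infer that the primary result is in doubt. It is not; Sections 9.1 and 9.4.2 state baseline outright.
- A reader might infer that Aim 2 has two competing outcome definitions. It has one definition, given in five places, and one incomplete restatement.
- A reader might take the MADRS effect of d = 0.92 in Section 4.2 as the size of the discrepancy. That is a comparison with midazolam at two weeks, not a within-arm change by Day 9.

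**Conclusion.** Wrong as written, of minor severity. Section 9.4.1 sets a reference for change that does not match the listed secondary endpoints for PCL-5, MADRS, SDS, CGI-S, IES-R and QIDS-SR, and it cannot serve 5 of the 7 IES-R and QIDS-SR time points. Followed literally, it shifts each affected change value by P − B. Nothing firmer can be said about size, because the documents do not report the change over infusions 1 to 4 for these scales.

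The conclusion rests on two readings of the text: that baseline means before the first infusion, as the synopsis says, and that pre-WET is Day 9, as Section 9.4.1 and the schedule together give. All affected results are exploratory and descriptive. The Aim 2 wording is a clarification only.

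**What to change.** 1. In Section 9.4.1, state that change for the listed endpoints is calculated from the Day 1 pre-infusion baseline. Use percent change from baseline only where the plan already needs it, namely the CAPS-5 30% criterion; the endpoint lists ask for change, not percent change, on the other scales.
2. In the same paragraph, keep change from pre-WET but label it as an additional descriptive summary, limited to variables measured on Day 9 and afterwards.
3. As a minor clarification in Section 9.4.3, write the Aim 2 outcome as CAPS-5 change from baseline to 12 weeks from the start of WET, and align the Aim 2 heading with Sections 3 and 8.1.

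**Cost.** One paragraph in 9.4.1, and one phrase and one heading in 9.4.3. The schedule already collects the scores needed at baseline and Day 9, so no visits, participants or models are added. Section 9.4.1 already allows the SAP to be updated before database lock. The downside is that two sets of change values may appear for one measure, so every table must name its reference.

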9.4.2 ANALYSIS OF THE PRIMARY EFFICACY ENDPOINT(S)

The primary outcome is change in PTSD symptom severity from baseline to 12 weeks from the start of WET measured by the Clinician-Administered PTSD Scale for DSM-5 (CAPS-5) score at 12 weeks from the start of WET minus the CAPS-5 score at baseline. The analysis of the primary endpoint for this pilot study will be descriptive. The mean change in CAPS-5 score from baseline with corresponding 95% confidence interval will be reported.

9.4.3 ANALYSIS OF THE SECONDARY ENDPOINT(S)

- **Secondary Efficacy Outcomes (Exploratory):** In this early-phase study, analyses of secondary efficacy outcomes will be considered exploratory and hypothesis-generating. CAPS-5, PCL-5, MADRS, CGI and SDS scores will be collected weekly through 6 weeks after the start of WET from all

eligible participants, and thereafter until 12 weeks (up to weekly, as tolerated, ensuring assessment at the 12-week time point for all participants). All participants will be followed naturally for 12 weeks from the start of WET, in order to capture, descriptively, more gradual effects of WET and potential effects of the combination of ketamine + WET in all patients. Thereafter, they will be collected monthly through week 24 from start of WET or until loss of treatment response, for the subgroup of participants who demonstrate improvement on the CAPS-5 at the 12-week assessment. Aggregate scores prior to adding WET, during WET, and during the maintenance phase (weeks 3 onward) will be reported descriptively at each time point using the number observed, mean, standard deviation, median, and interquartile range. Individual patient trajectories on these measures will be plotted over time to explore treatment response and patterns in maintenance of response. Mean change in CAPS-5 scores from baseline and corresponding 95% confidence intervals, as well as the proportion of patients with $\geq 30\%$ improvement from baseline on the CAPS-5 will also be reported at each time point. In addition, linear mixed-effects models of these outcomes may be fit to compare mean scores over time. Mixed models will test for the inclusion of a random intercept for patient and fixed effects for week against a fixed intercept model using a likelihood ratio test after comparing each model fit statistic (i.e., Akaike information criterion, AIC) where the best fitting model is the model with the lowest corresponding AIC. Once fit is assessed, parameter interpretation will commence.

- **IES-R and QIDS-SR with past-24-hour recall** – collected only at baseline, before each ketamine infusion, 24 hours after the first infusion, and on the response to ketamine assessment day – will be examined descriptively.

The relationship between depressive symptoms and PTSD will be explored to assess whether worsening depressive symptoms correlate with worsening PTSD symptoms and whether there is any evidence that the worsening of one precedes the other. Scale scores of both measures will be plotted over time together to evaluate trends descriptively. Fixed and mixed effects regression models will also be explored to estimate effects and 95% confidence intervals.

- Finally, additional analyses might explore differences with a historical comparison group from our published repeated IV ketamine study for PTSD (Feder et al 2021).

Aim 2 (Exploratory): To evaluate whether ketamine-induced change in extinction learning predicts maintenance of ketamine response over time. We will use regression models to evaluate whether ketamine-induced change in extinction learning [improvement in extinction learning between two time points: (1) before infusions and (2) after four infusions (prior to starting WET), measured with the computerized online Extinction Learning Task, is associated with change in CAPS-5 at 12 weeks after the start of WET. A univariable model of ketamine-induced change on the extinction learning measure [discrimination between aversively conditioned (CS+) and safe (CS-) stimuli over the first six blocks of the task] and changes in CAPS-5 score will be examined. Beta coefficients and 95% confidence intervals will be reported. A significant association between greater ketamine-induced improvement in extinction learning and improvement in CAPS-5 scores will be considered supportive of Hypothesis 2.

Computational analyses: Loss expectancy ratings data from each trial of the online extinction task will be analyzed via a computational model of latent cause inference developed by Gershman, Niv, and colleagues.^{75,76} Importantly, this model has previously been shown to be able to explain individual differences in failure of extinction learning in both healthy volunteers and trauma-exposed individuals

with and without PTSD.^{75,76} In brief, the model posits that during learning, an individual attempts to infer which underlying (latent) cause is responsible for their observations, based on a combination of their previous experience and prior beliefs about causal structure of the environment. Prior beliefs about the causal complexity of the environment are governed by a single concentration parameter, alpha (α). The key model output submitted to further analysis is the likelihood for each participant of a model where α was allowed to be > 0 (favoring multiple causes), compared to a model where $\alpha=0$ (single cause responsible for all observations), quantified as a log Bayes Factor (logBF; higher values=greater likelihood of a multi-cause model). The analysis will be run in MATLAB,⁸⁴ using publicly-available code associated with Gershman and Niv's published work.^{75,76}

